3.1. Clinical Decision Guideline/Electronic Decision Support System Implementation

Prior to the initiation of the study, a previously derived Clinical Decision Guideline (CDG) for ordering influenza testing was fully integrated into the site's electronic medical record (EMR) utilizing an Electronic Decision Support System (EDSS). This EDSS has now been integrated into the EMR at the Johns Hopkins Hospital (JHH) and at the Maricopa Medical Center (MMC) to inform clinician practice. This systematic influenza screening and testing program is part of the standard ED practice for recognition and management of patients with suspected influenza.

3.1.1. Clinical Decision Guideline

The previously derived and validated CDG will guide influenza testing in ED patients as follows:

A patient will be indicated for influenza testing with Xpert Flu if he/she has a symptom score of 3 or greater. The symptom score is based on the following:

- Within the past 7 days, new or worsening cough (2 points)
- Within the past 7 days, new headache (1 point)
- Within the past 7 days, new subjective fever (1 point)
- Documented temperature at triage of 38°C (100.4°F) or greater (1 point)

3.1.2. Electronic Decision Support System

Working collaboratively with a locally determined team (e.g., physicians, nursing, and information technology (IT) staff), the clinical pathway using an EDSS with the CDG has been integrated into the clinical flow and EMR to prompt influenza testing at initial triage. The overall flow of the EDSS is depicted in Figure 1. The EDSS will begin functioning in October of each influenza season.

[figure not shown]

Figure 1: EDSS flow for influenza testing

The EDSS will evaluate if the patient should receive influenza testing by screening for the criteria of the CDG. To determine if the patient is indicated for Xpert Flu testing, a triage nurse will be prompted (at triage) to complete the brief series of questions outlined above. If the testing is not indicated by the CDG (i.e., a score of less than 3), then there is no further action related to this EDSS. If the patient is indicated for influenza testing according to the CDG (i.e., a score of 3 or greater), then the EDSS will automatically generate a prompt stating that the Xpert Flu test is indicated for this patient. If the triage nurse orders the Xpert Flu test, an NP swab will be performed, and the specimen will be sent to the laboratory for processing. Alternatively, if the influenza test is not ordered, the triage nurse will be prompted to enter one of the following reasons for not testing: "Patient refused"; "Patient diagnosed with influenza within previous 48 hours"; or "Other, (insert text)."

For any patient receiving an Xpert Flu test through the EDSS, the result of the test will be recorded in the EMR when complete. Turnaround time (TAT) from placing the order to result received in the EMR will be tracked and it is anticipated that the laboratory will achieve TATs of less than 120 minutes (based on historical experience). However, while this is the expectation, if it is not met it does not constitute a protocol violation, as the influenza testing is part of routine care.

Providers may choose to treat or not treat patients as is clinically indicated.

3.1.3. Run-In Period

Beginning in October and running through April 30 of each influenza season or later, at the co-principal investigators' (Co-PIs') discretion, based on influenza prevalence, all ED patients who are assessed at triage will be evaluated by the CDG and EDSS to determine if they meet the testing criteria of the CDG. To evaluate whether or not the CDG and EDSS are being properly implemented, there will be a run-in period during October of each influenza season. The purpose of this run-in period is to identify and correct any potential problems with implementation of the CDG and EDSS. Principal investigators (PIs) and research staff will closely monitor the implementation of the CDG and EDSS through a standardized monitoring and continuous quality improvement (CQI) process.

During the run-in period, research staff will monitor implementation of the CDG and EDSS to ensure that registered ED patients are screened, and if they meet testing criteria, ensure that the order is placed and the test occurs. Research staff may be on site to act as a resource or to troubleshoot if any problems arise.

Ongoing monitoring will occur throughout the study period (November 1 – April 30 of each influenza season, or later, at the Co-PIs' discretion, based on influenza prevalence). Additionally, the Biomedical Advanced Research and Development Authority (BARDA) personnel will periodically conduct an independent audit to provide relevant feedback which will be informative for guiding future clinical trials.

3.2. Biological Specimens

3.2.1. Safety Precautions

All safety guidelines of the local safety committee and/or institutional policies for handling biological specimens must be followed. Universal precautions guidelines are to be observed.

3.2.2. Sample Collection

From each patient who is indicated for Xpert Flu testing by the CDG through the EDSS, an NP sample will be collected by clinical staff according to standard of care practice, using a flocked swab and universal viral transport media, as is standard clinical practice. All staff collecting NP swabs must undergo appropriate training as required by the medical institution. Once collected, specimens will be transported to the hospital clinical virology laboratory and expeditiously processed according to institutional laboratory protocols.

3.2.3. Sample Processing and Labeling

Between November 1 and April 30 of each influenza season, following sample collection, one aliquot will be removed for immediate rapid testing using Xpert Flu. A sterile pipette, will be used to aliquot the remaining specimen into approximately five 0.5 mL aliquots. Each aliquot will be placed in a separate microtube and labeled with a Waste Specimen identification number and date of collection. These aliquots will be immediately stored in a -80°C freezer until shipment (a log sheet will be maintained on the freezer or in another specified area in the laboratory to

indicate waste sample number, collection date/time, storage time). Freezer boxes will be labeled with “BARDA ED FLU PILOT RCT,” the collection site, and the lowest waste specimen identification number included in that freezer box. If samples go outside of range minus -20°C, the samples will be considered compromised and the Coordinating Center must be notified immediately.

3.2.4. Clinical Use of Waste Specimens

Leftover samples will be batched, shipped to, and stored at the central study laboratory at JHH for future analysis (see Appendix 2). These de-identified samples and results will not be available for clinical care.

4. Screening, Enrollment, and Follow-Up of Study Subjects

This section describes the screening, enrollment and follow-up procedures for the:

1. Retrospective Chart Review; and the
2. Randomized Controlled Trial of Influenza Antivirals.

During the 2015-2016 influenza season, this study was implemented only at JHH. During the 2016-2017 influenza season, this study will operate at both JHH and MMC.

4.1. Retrospective Chart Review

In order to evaluate the full potential ED population who might have met criteria for enrollment, all potentially eligible patients will be evaluated via a retrospective chart review. Basic demographic characteristics of patients who were not approached for enrollment, and those who were approached but not enrolled, will be compared (in a de-identified manner) with those who were enrolled into the Randomized Controlled Trial of Influenza Antivirals.

4.1.1. Screening

Research staff will identify subjects by retrospectively screening all ED patient records who presented between November and April of each influenza season, or later, at PI discretion, based on influenza prevalence, for patients who meet all eligibility criteria. Basic presenting, demographic, and eligibility information will be recorded on the Screening and Enrollment Log for every patient who is screened for potential enrollment. Patients that do not meet inclusion criteria will be excluded from the Retrospective Chart Review; the reason for exclusion will be recorded.

4.1.2. Eligibility Criteria

Inclusion Criteria

Full ED chart review will be performed on individuals who meet the following inclusion criteria at the time of the ED visit:

- 1) 18 years of age or older;
- 2) Adult ED visit between November and April of each influenza season, or later, at the Co-PIs' discretion, based on influenza prevalence; and
- 3) Positive influenza test associated with the ED visit

Exclusion Criteria

There are no exclusion criteria.

4.1.3. Informed Consent

Under a HIPAA waiver of consent, research staff will review patient charts to screen and confirm enrollment eligibility. This retrospective evaluation utilizes information that is already collected for clinical purposes and all data collected for the retrospective chart abstraction will ultimately be stripped of personal identifiers (see section 4.1.4).

4.1.4. Data Collection

For all eligible patients, research staff will review the ED and hospital records to retrospectively complete a set of structured clinical data forms to collect the following: basic demographic data; symptoms related to the CDG; criteria for CDC antiviral treatment; initial presentation and clinical course at the ED, including antiviral treatment, antibiotic treatment, Xpert Flu test or other influenza test information; and hospital course if subsequently admitted.

In accordance with HIPAA regulations, no subject personal identifiers will be entered into the study database. Personal identifiers such as name and medical record number will be collected and recorded on a separate study identification (ID) sheet for purposes of completing the retrospective chart review. This identifying information will be linked to the remainder of the subject information only through the study ID number, and will ultimately be stripped of identifying information after all necessary data and samples are collected. Personal identifiers will be destroyed upon final completion and verification of the study database.

All study documents will be kept locked in a limited access area. The study ID sheet that links the study ID numbers to the subject personal identifiers will be kept under double lock separate from all research files, accessible only to research staff.

4.2. Methods: Randomized Controlled Trial of Influenza Antivirals

4.2.1. Eligibility Criteria

Inclusion Criteria

To be considered eligible, patients must meet the criteria listed below at the time of screening:

- 1) 18 years of age or older;
- 2) Laboratory-confirmed positive influenza test associated with their current ED visit;

- 3) Presence of at least 1 of the following symptoms of acute respiratory illness for ≤ 4 days (96 hours):
 - a. New or increased cough;
 - b. New or increased shortness of breath;
 - c. Change in sputum production (for adults 65 years of age or older);
 - d. Sinus pain;
 - e. Nasal congestion;
 - f. Rhinorrhea;
 - g. Sore throat;
 - h. Subjective fever; or
 - i. Documented fever of $\geq 38^{\circ}\text{C}$.
- 4) Meets at least one of the CDC criteria for antiviral treatment, defined as:
 - a. 65 years of age or older;
 - b. Pregnant* or less than two weeks postpartum;
 - c. American Indian or Alaska Native;
 - d. Morbid obesity (body mass index (BMI) ≥ 40);
 - e. Current resident of nursing home or other chronic-care facility;
 - f. Diagnosis of chronic pulmonary disease, cardiovascular disease (except hypertension alone), renal disease, hepatic disease, hematologic disease, metabolic disorders, neurologic and neurodevelopment conditions, or immunosuppression (including that caused by medications or by human immunodeficiency virus (HIV) infection);
 - g. Admission to inpatient or an observation unit; or
 - h. Clinical diagnosis of pneumonia (by the ED provider)

*For the purpose of this study, pregnancy is an exclusion criterion.

Exclusion Criteria

To be considered eligible for enrollment, a patient must not meet any of the criteria listed below at the time of screening:

- 1) Does not speak or understand English (JHH); or English or Spanish (MMC);

- 2) Unable or unwilling to provide informed consent;
- 3) Previously enrolled in the study during the current influenza season;
- 4) Unable to take oral medication;
- 5) Unable to comply with all planned study procedures including availability for follow-up and willingness to complete study diary and self-assessment;
- 6) Use of neuraminidase inhibitors within the past seven days;
- 7) Known allergic reaction to neuraminidase inhibitors;
- 8) Pregnant or breastfeeding;
- 9) End-stage renal disease, defined as:
 - a. Currently undergoing dialysis (either hemo or peritoneal); or
 - b. Creatinine clearance (CrCl) of <10 mL/min.
- 10) End-stage liver disease, as determined by the treating ED provider;
- 11) Glucose-6-phosphate dehydrogenase (G6PD) deficiency by patient report;
- 12) Immunodeficiency, defined as:
 - a. Solid organ transplant patients receiving immunosuppression;
 - b. Hematopoietic stem cell transplant patients within 12 months of transplant or with ongoing immunosuppression;
 - c. Oncology patients who have had chemotherapy within the past 30 days;
 - d. Current treatment with steroids equivalent to 10 mg of prednisone or more per day for greater than two weeks;
 - e. Rheumatologic patients receiving immunosuppressive therapy; or
 - f. HIV patients who meet one of the following criteria:
 - i. Have a CD4 cell count of <200 cells/mm³ within the past 3 months;
 - ii. Not actively receiving highly active antiretroviral therapy (HAART); or
 - iii. Have an absolute lymphocyte count <1.0 x 10³ cells/µL conducted at the current ED visit

4.2.2. Screening

Eligible subjects will be recruited by dedicated research staff 24 hours a day, 7 days a week. Screening and enrollment occur at the same visit.

Under a HIPAA waiver of consent, research staff will review current ED patient charts for adult ED patients who have a positive laboratory-confirmed influenza test during their current ED visit. If a patient appears to be eligible, the research staff will approach the patient's ED provider to inform them that the patient is potentially eligible. Alternatively, providers may also refer potentially eligible patients to research staff. With the provider's approval, research staff will approach the patient, verify that the patient meets eligibility criteria, and determine if he/she would like to participate in the study.

Eligibility information will be recorded for every patient who is approached for potential study enrollment using a Screening and Enrollment Log. Patients who do not meet inclusion criteria or who meet an exclusion criterion will be deemed ineligible; the reason for their exclusion will be recorded. Screened patients who meet all inclusion and no exclusion criteria, i.e., who are eligible, will be approached for informed consent. For those patients who decline participation, the given reason for refusal to participate will be recorded. Screened patients who are eligible and provide written consent to participate in the study, will be randomized to a treatment arm and considered as enrolled in the study.

4.2.3. Informed Consent

Consent forms will be IRB-approved and the patient will be given sufficient time to read and review the document and discuss it with his/her family member, friend, or legal representative. If he/she requires assistance to reach his/her family member, friend, or legal representative, such as the use of a telephone, that will be facilitated. After this, he/she will be specifically asked if he/she has any questions or concerns, which will be addressed, or would like more time to consider his/her participation, which will also be provided. The investigator or research staff will explain the research study to the patient and answer any questions that may arise. The patient will sign the ICF prior to any procedures being done specifically for the study. The subject may withdraw consent at any time throughout the course of the trial. A copy of the signed informed consent will be given to the subject for his/her records; another copy will be included in the patient's chart, and the original will be filed in a study binder. The rights and welfare of the subject will be protected by emphasizing to all potential study subjects that they will still be able to receive medical care at the facility if they decline to participate in this study. The site PI or designee will also sign the consent form indicating that the subject understands the risks and benefits of the study.

5. Study Visit Evaluations: Randomized Controlled Trial of Influenza Antivirals

5.1. Screening/Enrollment

Following written informed consent, the research staff will complete an eligibility checklist and assign a study ID number. The following information and evaluations will be performed:

5.1.1. Chart Review

Research staff will gather the following information:

- Basic laboratory studies:
 - Complete blood count (CBC);
 - Complete or basic metabolic panel; and
 - Serum (or urine) beta-hcg (for women of childbearing potential*).
- Calculate CrCl using the Cockcroft Gault equation (see Manual of Operating Procedures (MOP)); and
- Baseline chest x-ray.

*For the purposes of this study, women will be considered of non-childbearing potential if they are greater than age 54 and have had no menses in the previous 12 months or if they are surgically sterile (e.g., hysterectomy with or without oophorectomy; fallopian tube ligation; endometrial ablation).

In the majority of cases the above mentioned tests will be obtained for clinical purposes (at the time of enrollment or within the previous 24 hours). In cases where any of those tests have not been obtained, research staff will complete those tests as part of study procedures; results of these laboratory and/or imaging results will be given to the treating ED provider to include in his/her medical assessment of the patient. Patients with a CrCl <10 mL/min (or on hemodialysis), a positive beta-hcg, or those who did not have the appropriate laboratory studies performed, will be ineligible for enrollment and will not be randomized to receive antiviral treatment through this study.

5.1.2. Clinical Evaluations

Demographics and clinical data (medical and health history) will be collected using brief structured data forms and will include:

- Basic demographic data;
- Vaccination history;
- Co-morbid illness;
- History of present illness;
- Baseline PGIS; and the
- First day of the validated Daily *FLU-PRO Symptom Questionnaire (F10)* and the *Functional Assessment (F12)* form.

5.1.3. Treatment Assignment Procedures

All eligible subjects will be randomized to receive one of two treatment groups using a computerized randomization system in the ratio of 1:1. Subjects will be randomized to receive either oral or IV antiviral treatment. Randomization will be performed by research staff after informed consent, laboratory results, and verification of all eligibility criteria have been performed (see MOP).

5.1.4. Treatment Administration

Subjects will begin their treatment regimen in the ED as described below:

Oseltamivir

Subjects randomized to the oral treatment arm will receive oral oseltamivir. Oseltamivir will be dosed based on CrCl results, as described below.

CrCl Result	Dosage of Oral Oseltamivir	Frequency/Duration
>60 mL/min	75 mg	Twice daily (every 12 hours) for 5 days
>30 – 60 mL/min	30 mg	Twice daily (every 12 hours) for 5 days
>10 – 30 mL/min	30 mg	Once daily (every 24 hours) for 5 days

The first dose will be administered in the ED following randomization. The remaining doses will be taken on the subsequent four days, whether they are inpatient or outpatient, based on the screening CrCl results. If a dose is missed, subjects will be instructed to take the missed dose as soon as they remember, unless it is two hours or less before the next scheduled dose; in this case, subjects will be instructed to discard the missed dose, and continue to take the next dose at the usual time. Subjects will be instructed not to take two doses at a time to make up for a missed dose.

Peramivir

Subjects randomized to the IV treatment group will receive IV peramivir. Peramivir will be dosed based on CrCl results, as described below.

CrCl Result	Dosage of IV Peramivir	Frequency/Duration
≥50 mL/min	600 mg	One time
30 – 49 mL/min	200 mg	One time
10 – 29 mL/min	100 mg	One time

Subjects in the IV treatment arm will receive a single dose of IV peramivir in the ED following randomization. If the subject does not have an IV line, one will be placed by the clinical staff. If the clinical team's plan is for the subject to be discharged home from the ED, he/she will receive no further study drug. If the clinical team's plan is for the subject to be admitted to the hospital, the subject's influenza treatment after leaving the ED will be up to the discretion of the inpatient treating provider. The inpatient treating provider will be informed of the subject's participation in the study and will be provided with the option to continue the use of IV peramivir at the same dose (based on CrCl result) for each subsequent day for up to four days. Treatment will stop upon discharge from the hospital. Should a subject remain in the hospital after five days of treatment, and the subject is symptomatically better, treatment will stop. If the subject remains hospitalized after five days of treatment and has not improved, the treating provider will have the option to continue the use of IV peramivir daily for another five-day course.

Study treatment, either oral or IV, may be stopped at the discretion of the treating provider should the provider believe that it is in the subject's best medical interest.

Treating providers of subjects who are admitted to the hospital will be provided with 24 hours a day/7 days per week access to an infectious diseases specialist, who will be available to consult on the use of peramivir and oseltamivir in admitted subjects.

5.1.5. Enrollment Completion

At the completion of all enrollment processes, subjects will be reminded that they need to complete a daily diary (to assess daily symptom severity, safety data, study drug adherence, as applicable, and provide a functional assessment) for 14 days between 3:00 PM – 11:59 PM local time. Subjects will be encouraged to complete the daily diary at the same time each day. Subjects will be reminded that research staff will be contacting them regarding daily diary entries and self-assessments, and at Days 3, 7, and 28 to collect follow-up information.

Subjects will also be asked to sign an authorization for release of health information which will allow research staff to obtain information on the subject's visits to other hospitals, should there be any subsequent medical encounters in the following 28 days.

Subjects who are discharged from the ED will be instructed to follow the ED standard discharge procedures.

5.2. Follow-Up

After enrollment (Day 1), subjects will be expected to complete a daily diary each day for 14 days, and complete "check-ins" on Days 3 and 7, and a follow-up assessment on Day 28. Research staff will also review the subject's medical records on Day 7 and Day 28.

5.2.1. Daily Diary

Beginning with the day of enrollment, for 14 consecutive days, subjects will be asked to complete a daily diary. The daily diary is expected to take approximately 10 minutes per day to complete, and will consist of the following 3 sections: 1) FLU-PRO Symptom Questionnaire

("Symptom Diary"); 2) medication adherence, side effect profile (including skin reactions and rash, neuropsychiatric events, nausea, vomiting, and diarrhea), and hospitalization history; and 3) a functional assessment.

Research staff will provide subjects with access to the web-based daily diary. The diary may be completed either by the subject via a secure web-based system that can be accessed from a personal web-enabled device, such as a laptop, personal computer, or tablet; or by personal contact (in-person or telephone) with trained research staff who will ask the questions and complete the web-based survey on behalf of the subject. If the subject is in the hospital, research staff will visit the subject daily to complete the diary.

Each day following enrollment, the research staff will review the subject's previous day's diary to verify whether or not the diary entry was completed. Missed diary entries cannot be made up. If a diary entry is missed, the research staff will call to remind the subject to complete the next diary entry as well as all remaining entries. Research staff may also offer to continue to contact the subject daily to assist the subject in completing the daily diary. If at any point the subject reports a skin reaction, rash, confusion, or hallucinations, research staff will immediately call to instruct the subject to return to the ED for evaluation (see section 7.2).

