3.4.2 Safety

Safety will be assessed by evaluating the clinical significance of laboratory abnormalities and AEs and all serious adverse events SAEs. The overall occurrences of AEs and SAEs will be reported by SOC and PT. The AEs and SAEs will also be evaluated and reported by the relationship to study drug, severity and the outcome. All the results will be summarized by study arm and/or by clinical site as appropriate. Results will be presented in Tables 9 - 11 and Listings 1 – 3.

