The study will be conducted in accordance with Good Clinical Practice (GCP), and full compliance with 21 Code of Federal Regulations (CFR) Parts 11, 50, 54, 56, and 312; 45 CFR Part 46 (Protection of Human Subjects); and the HIPAA Privacy Rule. Procedures for managing protected health information (PHI) will be included in the written informed consent form (ICF). Numerous safeguards will be put in place to ensure the confidentiality and integrity of all data, addressing both the human and physical elements of protecting subject confidentiality. These include data management staff training in protection of human subjects and the ethical conduct of human research, systematic backup for the centralized database, use of encrypted data on durable media, and utilization of encryption and role-based access mechanisms for remote access in compliance with industry best practices and consistent with security and privacy requirements of the IRB. Any paper documentation containing PHI, such as informed consent documents, will be stored securely by research staff. See section 11.4 for further information on maintaining confidentiality to reduce PHI disclosure risks.

Depending on the randomization, a subject may receive oseltamivir or peramivir. According to the current package insert, the following warnings and precautions, drug interactions, and AEs are reported with these study drugs:

Oseltamivir (Tamiflu)

Warnings and Precautions:

Serious skin/hypersensitivity reactions such as Stevens-Johnson Syndrome, toxic epidermal necrolysis and erythema multiforme: Discontinue TAMIFLU and initiate appropriate treatment if allergic-like reactions occur or are suspected.

Neuropsychiatric events: Patients with influenza, including those receiving TAMIFLU, particularly pediatric patients, may be at an increased risk of confusion or abnormal behavior early in their illness. Monitor for signs of abnormal behavior.

Drug Interactions:

Live attenuated influenza vaccine (LAIV), intranasal:

Do not administer until 48 hours following cessation of TAMIFLU.

Do not administer TAMIFLU until two weeks following administration of the LAIV, unless medically indicated.

Adverse Reactions:

Most common adverse reactions (>1% and more common than with placebo):

Treatment studies – Nausea, vomiting, bronchitis, insomnia, vertigo.

Prophylaxis studies – Nausea, vomiting, diarrhea, abdominal pain.

Peramivir (Rapivab)

Warnings and Precautions:

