Serious skin/hypersensitivity reactions such as Stevens-Johnson Syndrome and erythema multiforme have occurred with RAPIVAB.

Neuropsychiatric events: Patients with influenza may be at an increased risk of hallucinations, delirium, and abnormal behavior early in their illness. Monitor for signs of abnormal behavior.

Drug Interactions:

LAIV, intranasal: Avoid use of LAIV within 2 weeks before or 48 hours after administration of RAPIVAB, unless medically indicated.

Adverse Reactions:

Most common adverse reaction (incidence >2%) is diarrhea.

This study is only enrolling subjects with confirmed influenza who are recommended to receive antiviral treatment according to current CDC guidelines, and treating them with appropriate

antiviral drugs which have been FDA approved to treat patients with influenza. The most commonly used antiviral treatment for influenza is oseltamivir, which is recommended by the CDC antiviral treatment guidelines. Oseltamivir has a low side effect profile, and has been shown to reduce the duration of symptoms in randomized control trials with outpatients and is approved by the FDA for treatment of uncomplicated influenza within 48 hours of symptom onset. Observational studies have shown that oseltamivir reduces mortality, hospital length of stay, and influenza-related complications in various high-risk groups. Peramivir, which is in the same neuraminidase inhibitor class as oseltamivir but is delivered in an intravenous (IV) formulation, has likewise been approved by the FDA for treatment of uncomplicated influenza within 48 hours of symptom onset. Peramivir also has a low side effect profile. There are insufficient studies to date, regarding the use of peramivir for hospitalized patients with influenza.

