8.1. Documenting, Recording, and Reporting Adverse Events

At each follow-up contact with the subject (i.e., phone call follow-up for outpatient and in-person follow-up for inpatients), information regarding AEs and unanticipated problems will be elicited by appropriate questioning and will be documented and reported as outlined below.

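### The SAP summarises none of the side-effect answers solicited daily in the diary, and neither document says when such an answer becomes an adverse event

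*Combined protocol and SAP*

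**What the plan says.** **Collection.** Protocol 5.2.1: "Beginning with the day of enrollment, for 14 consecutive days, subjects will be asked to complete a daily diary". The diary has three sections. The second covers adherence, hospitalization history and a "side effect profile (including skin reactions and rash, neuropsychiatric events, nausea, vomiting, and diarrhea"). Nothing restricts these items to one arm. Protocol 5.1.5 gives the diary's purpose as "to assess daily symptom severity, safety data, study drug adherence, as applicable, and provide a functional assessment".

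**Why these items matter.** Protocol 1.2.1 lists the common reactions in oseltamivir treatment studies as "Nausea, vomiting, bronchitis, insomnia, vertigo". For peramivir it says "Most common adverse reaction (incidence >2%) is diarrhea".

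**AE capture.** Protocol 8.1: "At each follow-up contact with the subject (i.e., phone call follow-up for outpatient and in-person follow-up for inpatients), information regarding AEs" is elicited and documented. The scheduled contacts are Days 3, 7 and 28. Protocol 8.1.1 sends AEs to form F20.

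**Analysis.** SAP 3.4.2 bases safety on laboratory abnormalities, AEs and SAEs: "Results will be presented in Tables 9 - 11" and Listings 1 to 3. The outcome list in SAP 2.3.1 does not name the diary's side-effect profile.

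**The concern.** The diary puts the same side-effect questions to both arms on the same daily schedule, and they include the reactions that the protocol itself names as most common for each drug. If the SAP is followed as written, the answers are collected and never shown.

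The AE tables may or may not contain them. Without a rule for when a diary answer becomes an AE, two sites could both comply with the protocol and treat the same report of vomiting differently. Handling could also differ by arm. Protocol 6.6 has staff read diary content daily to track oseltamivir adherence, in the section that also holds the side-effect items, and describes no matching adherence review for peramivir. It could differ by setting too, since inpatients are visited daily while discharged subjects may complete the diary online.

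The stake is modest but relevant. SAP 2.1 says the pilot is meant to show that useful endpoint data can be collected reliably from an ED, and a later trial would want the proportion of each arm reporting nausea, vomiting or diarrhea.

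**Working it through.** This is a question of coverage, so the main check sets diary content against SAP output.

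**1. Where each part of the diary goes**

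- FLU-PRO symptoms: Table 4 and Figure 2.
- Functional assessment: apparently the Karnofsky rows of Table 5 and Figure 3.
- Diary completion: a row in Table 3.
- Adherence: abstracted to form F24 (Protocol 6.6). Table 3 has a row for number of doses.
- Side-effect answers: 0 of 11 tables, 0 of 5 figures, 0 of 3 listings.

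**2. Whether a neighbouring table supplies the same information**

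- Table 4 has a gastrointestinal row by arm, but it shows mean, standard deviation and range of a severity score. The number of subjects with vomiting or diarrhea cannot be recovered from it.
- Table 9 counts subjects with AEs by arm and preferred term. It would show vomiting only if someone entered it on F20.
- Table 11 has rows for allergy/hypersensitivity, rash or skin reaction, and altered mental status. It has no gastrointestinal rows and a single N (%) column, so no split by arm.

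**3. Whether a route from diary to F20 is stated**

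- Protocol 5.2.1 describes the daily review as checking that the previous day's entry was filled in. A call follows only for rash or other skin reaction, confusion or hallucinations.
- Protocol 6.6 shows that, where transfer from diary to form is intended, the protocol can say so (adherence to F24). No matching sentence covers side effects and F20.
- Protocol 8.1.1 requires all on-study AEs to be documented, but does not say when a diary answer counts as one.

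**4. Volume of data**

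Protocol 9.3 anticipates 225 subjects. Diary entries: 14 × 225 = 3,150 at most. Scheduled follow-up contacts: 3 × 225 = 675, of which 2 × 225 = 450 (Days 3 and 7) fall inside the diary window.

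**5. Whether a table by arm would be informative**

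The plan's own enrollment estimate reproduces: 311 × 0.75 × 0.75 = 174.9 eligible (stated 174), and 174 × 0.56 = 97.4 enrolled (stated 97). With 1:1 allocation, n per arm is 97/2 = 48.5 or 225/2 = 112.5.

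The documents give no incidence for the diary effects, so 5%, 10% and 20% are assumed. The 95% half-width within an arm is 1.96 × √(p(1−p)/n). For p = 0.10 and n = 112.5 this is 1.96 × √(0.09/112.5) = 0.055.

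| Assumed incidence | N = 97 | N = 225 |
|---|---|---|
| 5% | ±6.1 points | ±4.0 points |
| 10% | ±8.4 points | ±5.5 points |
| 20% | ±11.3 points | ±7.4 points |

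That is adequate for description and planning. It does not support a test between arms, and none is planned.

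**The case against.** The strongest reply is that the AE system already covers these effects. A good part of it stands:

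- All on-study AEs must be documented (Protocol 8.1.1), and section 7 accepts that they may surface during or after any study procedure or interview.
- Staff call every subject on Days 3 and 7 specifically about tolerability and AEs (5.2.2).
- Inpatients, about 40% of those enrolled (8.1.2), are visited daily, and diaries may be completed by staff interview (5.2.1).
- Subjects can contact the team about a possible AE throughout the trial (1.2.1).
- Appendix 1 says staff review the diaries each day, without limiting this to completion.

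A reader might therefore infer too much in saying that tolerability by arm rests only on AEs raised at a few contacts, or that the diary is the only systematic tolerability data. The documents support neither. A diary report can reach Table 9. What is missing is a stated route.

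A reader might also want to put a number on under-counting in Table 9. The documents give neither a true incidence nor a capture rate, so any such figure would be assumption alone.

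Three further points stand. The trial is a descriptive pilot with no comparison between arms, and tolerability by arm is not a listed outcome. The Manual of Operating Procedures, to which the protocol refers for diary procedures and which is not among these documents, may contain the transcription rule. Diary answers are open-label self-reports, so tabulating them does not remove reporting bias.

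None of this supplies the missing summary. Even perfect AE recording would not show the diary answers themselves.

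**Conclusion.** The gap is real and limited. Solicited side-effect answers, collected daily for 14 days in both arms as safety data, have no summary anywhere in the SAP, and neither document defines how they become AEs. Gastrointestinal tolerability by arm is therefore left to AE recording whose link to the diary is undefined.

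The size is one of coverage: none of the 19 planned outputs (11 tables, 5 figures, 3 listings) shows these items. How far the AE tables would differ from the diary cannot be estimated from the documents. The sample size, the primary feasibility outcomes and the decision not to test between arms are unaffected.

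The conclusion assumes that the side-effect section is completed in both arms as Protocol 5.2.1 describes. If the Manual of Operating Procedures holds a transcription rule, that part of the point reduces to citing it in the SAP. The missing table remains. This is a cheap improvement.

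**What to change.** 1. Add to SAP 3.4.2 a descriptive table by arm: number (%) of dosed subjects with at least one completed diary who report each solicited effect (nausea, vomiting, diarrhea, skin reaction or rash, neuropsychiatric event), over Days 1–14 and over Days 1–5. Show diary-days completed alongside, because missed entries cannot be made up. Label the counts *reported*, not *drug-related*.
2. Add arm columns to Table 11.
3. State in the SAP or protocol whether diary reports are transcribed to F20 and, if so, by whom and on what criterion. If the rule is already in the Manual of Operating Procedures, cite it.
4. Separate effects already present on Day 1 only if the sponsor confirms that the side-effect section is completed before dosing. Protocol 5.1.2 and Appendix 1 name only the FLU-PRO (F10) and functional (F12) forms for the ED, so a pre-dose baseline for these items cannot be assumed.

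The cost is programming one table from data that the diary already collects, plus a few sentences of text. It needs no new data, test or sample-size change. The small downside is interpretive: counts will mix gastrointestinal symptoms of influenza with drug effects and remain open-label self-reports. A footnote should say so.
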